Eye movement and dilation in response to attentional-shift requiring tasks will be used to measure ATX drug action in the CNS. The tasks are based on a modified Posner Cuing Task, which measures both endogenous and exogenous orientation of attention, which correspond to tonic and phasic locus coeruleus activation. This is an established non-invasive method to measure norepinephrine signaling in the brain. Assessment will take place at both the ADHD Specialty clinic and at the PCRU. Participants will be asked to sit 57 cm from a computer monitor, which is housed in a light dome to maintain a consistent level of illumination. Volunteers will be asked to place their chin in a mounted chin rest to stabilize the facial area. Each study participant will be asked to complete target localization and target discrimination tasks. Both tasks begin with the participants looking at two white squares on black background. In between these two boxes will be a white fixation cross. Participants will be asked to begin each trial by focusing on the fixation cross. Next, a cue is given. In this case, one of two boxes brightening will serve as the cue. Following the cue, a target will appear in one of the two boxes by presentation of an “O” or a “Q” in one of the two boxes. Participants will be asked to push colored buttons on the game controller that correspond with the correct answer when presented with the target. If the target appears in the box that was brightened, this is defined as a valid trial. When this does not occur, this is considered an invalid trial. Half of the trials will be designed to be invalid. The valid and invalid cues serve to measure directing of attention by study participants. Volunteers will be measured for their ability to localize the target (e.g. did the target appear on the left or right box?) and discriminate the target (e.g. is the target a “Q” or an “O”?) following the cue. In localization tasks, if the target appears on the left side, volunteers will be asked to push the blue button. When the target is on the right side, a successful trial would mean the volunteer pushed the red button. In discrimination tasks, if the target presented is a “Q” the volunteer will be asked to push the red button, while an “O” target means the volunteer should press the blue button. Volunteers will be given

the opportunity to practice the tasks (3 trials). Measurements will be recorded for 162 trials which for both localization and discrimination tasks. Eye-moment, dilation, and reaction time will be measured during all tasks. Please see **Figures 1 and 2** in the Appendix H of this document. **Figure 1** illustrates an example of a valid and invalid trial for successful completion of the localization task, while **Figure 2** illustrates an example of a valid and invalid trial for successful completion of the discrimination task.(Aston-Jones and Cohen, 2005; Alnaes et al., 2014)

Secondary Study Endpoints:

The secondary aims focus on: exploring baseline patient characteristics that may predispose an individual to have beneficial clinical response from ATX therapy; refinement of the iGO-PK dosing algorithm; exploration of the role of the microbiome in impacting ATX pharmacokinetics and pharmacodynamics; validation of a urinary CYP2D6 biomarker; and exploring ways improve study participant understanding of research procedures. A previous study with an anti-depressant, citalopram, suggests that the ability to respond positively to a medication may be predicted given an understanding of the individuals' composite of signaling molecules, i.e. the global neurotransmitter profile. We are interested in comparing the baseline global neurotransmitter profile between children who do and do not respond. We are also interested in understanding how the neurotransmitter profile changes with chronic ATX use and correlating these changes with clinical benefit of toxicity. To do this, we will evaluate a panel of approximately 30 neurotransmitters (Gupta et al., 2016)(refer to Appendix I for example list) prior to treatment and during treatment with ATX.

Because there is evidence that the gut microbiome can to influence host neurotransmitter concentrations (Petra et al., 2015), we would like to evaluate this as a possible confounder to the global neurotransmitter profile. Given that the oral and gut microbiome landscape correlate well with one another (Zhang et al., 2015) we will also sample saliva to account for factors that could contribute to an individual's neurotransmitter make-up.

The pharmacokinetic data that we collect on each individual participant allows us to provide more information for modeling, and for further refinement. We recognized in our previous pharmacokinetic study that CYP2D6 activity, as measured using a phenotypic marker (urinary dextromethorphan/dextrorphan ratio), was the best predictor of ATX exposure. This urinary ratio was associated with ~75% of variability observed in ATX exposure in the study. We would like to explore a urinary biomarker that is reflective of CYP2D6 activity that has previously been studied (Tay-Sontheimer et al., 2014) for possible inclusion in the iGO-PK model. Validation of this biomarker with ATX exposure is necessary prior to consideration as a variable in the iGO-PK algorithm.

Lastly, we recognize that our patient population will include young children and that lengthy consent forms may not be optimal for conveying information. We plan to

distribute a supplemental illustrated booklet (please refer to Supplementary Documents, “U54 Study Booklet”) explaining study procedures along with a standard consent form to all participants approached for the study. A short questionnaire will accompany the booklet, asking study participants and their families to evaluate the study booklet (please refer to Appendix G) in helping with their clarity and comprehension of the study.

#### 4.2 Primary Safety Endpoints

Participant baseline health, including behaviors, will be recorded at Research Visit 1 with a physical exam, baseline electrocardiogram, medical history, and concomitant medication history. Additionally, baseline health and behavior data will be captured at the Intake Visit with the Study Physician. Adverse events will also be closely monitored. These are defined by Children’s Mercy Hospital Reportable Events Research Policy and Procedures as “untoward or unfavorable occurrences in a human subject, including an abnormal sign [e.g., abnormal physical exam or laboratory finding], symptom, or disease, temporally associated with the subject’s participation in the research, whether or not considered related to the subject’s participation in the research.” Additionally, an adverse event is also defined as behaviors or symptoms that occur with increased frequency or severity as consequence of the subject’s participation in the research study.

Both types of adverse events will be documented in this study. Adverse events are reported in many ways in this study. These include but are not limited to: emails to study coordinators/clinical trial manager, phone calls on study cell phone, phone calls to ADHD Clinic or Developmental and Behavioral Clinic, reported to study physician at clinic visit, reported on Medication Side Effects questionnaires, reported at research visits when asked, or via a Cerner notification of admission to the hospital to the study physician. Additionally, adverse events will be assessed and documented at Research Visit 2, Research Visit 3, Research Visit 4, 6-week Visit, 12-week Visit, and 18-week Visit.

Adverse events will be categorized and reported to the IRB as outlined in CM Policy regarding adverse events. These events will be documented consistently, regardless of how they were reported. This includes the delegation of an individual member of the study personnel to handle all adverse event reporting. All adverse events will be recorded at all research visits and in between visits as needed on the Adverse Event CRF kept in the subject’s study binder.

In addition, subjects will be classified based on their tolerance of ATX. A participant is considered tolerant of ATX if the side effects did not lead to discontinuation of ATX therapy. A participant is considered intolerant of ATX if the side effects lead to the discontinuation of medication and withdrawal of a subject from the study.

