### **8.2 Target Participants**

The research proposal targets 160 participants who are expected to be enrolled and screened. The target number of subjects needed to complete research procedures is 120. Participants who complete at least Research Visits 1-3, the Intake Visit, and the 6-Week Visit with the Study Physician will be considered to have "partially completed" the study. Completion of these visits will include obtaining baseline measurements, confirmation of eligibility, single and steady-state PK and PD measurements, and at least one post-treatment clinical response assessment. Since data from these participants will meet the study aims, those who partially complete the study will be counted toward the 120.

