## 20.0 Data Management

### 20.1 Data Analysis Plan

#### Population to be Analyzed:

- The pharmacokinetic population will consist of all participants with sufficient plasma concentrations for calculation of all pharmacokinetic parameters.
- The pharmacodynamic population will comprise of all patients with sufficient DHPG plasma concentrations, adequate data from pupil dilation and eye-tracking measurements, and cardiovascular measures (heart rate and blood pressure). Additional metabolites analyzed via metabolomics platform will also be analyzed (as discussed below).
- All participants who meet criteria for determination of both pharmacokinetic and pharmacodynamic parameters and have at least partially completed the study will be evaluated for pharmacodynamic linked clinical outcomes analysis. A partial completion is any participant where at least Research Visit 1, Research Visit 2, Research Visit 3, Intake Visit with Physician, and 6-week Visit with Study Physician have been completed. Clinical outcomes will be analyzed in four ways:
  - Response: responder vs. non-responder
  - Toxicity: tolerant vs. non-tolerant
  - Adherence: low, medium, and high
  - Adverse event reporting
- In addition, all participants for which demographic and background characteristics and concomitant medication history were collected will be analyzed.
- All completed and returned U54 Study Booklet questionnaires and surveys will be used to assess the effectiveness of the U54 Study Booklet in study comprehension. Feedback from the survey will be compiled for analysis.

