#### Pupillometry Analysis:

Changes in performance during Posner Cuing Task will be measured as a function ATX exposure and  $C_{max}$  concentrations. Pupil size will be measured during two types of activities: localization and discrimination tasks. Pupil size differences during localization tasks report on the individuals' baseline (tonic) release of norepinephrine. This corresponds to endogenous, or volitional attention. Pupil size differences during discrimination tasks is a composite of the individuals' baseline (tonic) and situational (phasic) release of norepinephrine. Currently it is unclear whether tonic, phasic, or both are impaired in individuals with ADHD.

Cardiovascular Marker Analysis:

Changes in heart rate will also be measured as a function ATX exposure and  $C_{max}$  concentrations. One side effect of ATX that is directly related to the pharmacodynamics of the drug is an increased heart rate due to increased concentration of norepinephrine in blood. We would like to understand the extent of this side effect as a function of increased systemic ATX exposure and  $C_{max}$ . By studying these two components, we will be able to distinguish ATX drug action in central and peripheral nervous systems.

Pharmacodynamic Changes Correlated with change in NICHQ Vanderbilt Assessment Scales:

All changes markers of pharmacodynamic action will be correlated with whether a child is classified as a responder or non-responder; and tolerant or intolerant (see Clinical Outcomes below for details). Extent of adherence will be used as a confounding factor in both of these analyses.

Clinical Outcomes:

Determine and document participant response to ATX therapy:

- Responders will be defined as:
  - Participants, who after approximately 18 weeks of continuous treatment with ATX, demonstrate  $\geq 40\%$  reduction of baseline ADHD symptom score;
  - OR the Clinical Global Improvement rating is 1 or 2 (Very Much Improved or Much Improved).
- Non-responders will be defined as:
  - Participants, who after approximately 18 weeks of continuous treatment with ATX, demonstrate  $< 40\%$  reduction of baseline ADHD symptom score, AND the Clinical Global Improvement score  $\geq 3$ .
  - Participants who discontinue ATX prior to the planned end of study (18 weeks) due to perceived lack of efficacy despite dose escalation.

Determine and document participant tolerance of ATX therapy:

- ATX intolerant participants are:

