  - Participants who present with side-effects that significantly interfere with daily functioning or outweigh therapeutic benefit (CGI Efficacy Scale categorization)
  - Participants who must discontinue ATX for any of the following reasons: AST or ALT three times the upper limit of normal (ULN) for age, alkaline phosphatase five times the ULN, total bilirubin two times ULN, QT prolongation or dysrhythmia, hypertension (systolic or diastolic BP above 95% for age), tachycardia (HR above 95% for age)

Parent and teacher responses for the NICHQ Vanderbilt Assessment Scales will be obtained at baseline and  $\pm$  2 weeks of 6-week Visit with Study Physician, 12-week Visit with Study Physician, and 18-week Visit with Study Physician. If questionnaires are returned outside of this window, or are unreturned, these will be considered, "missing data." Determination of response, i.e. responder vs. non-responder, will be done using parent responses to questionnaires. Teacher response to questionnaires will also be analyzed to evaluate symptom reduction in a secondary setting. Partial return of teacher questionnaires are still useful in that these data may be used to correct for bias in parental response.

Questionnaires conducted at baseline and at either 18-week visit with Study Physician or a Research Visit will be analyzed for change pre- and post-intervention. These include: BRIEF – parent, SCT, SCARED, CBCL, and School Intervention Questionnaire.

Statistical analyses of clinical response in the population studied will be performed by The Division of Health Services and Outcomes Research at the Children's Mercy Hospital, Kansas City, MO. SAS version 9.4 (SAS, Cary, NC, USA) and R (The R Foundation) will be used to determine if ATX responders and non-responders can be differentiated by a subset of patient specific covariates.

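### Tolerance is a yes/no label with no assessment time, so children followed for about 6 weeks are pooled with children followed for about 18

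*Combined protocol and SAP*

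**What the plan says.** **Definition in section 4.2.** The section says: "A participant is considered tolerant of ATX if the side effects did not lead to discontinuation of ATX therapy". It continues: "A participant is considered intolerant of ATX if the side effects lead to the discontinuation of medication and withdrawal of a subject from the study". Neither sentence has a time element.

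**Definition in section 20.1, Clinical Outcomes.** Intolerance here is wider. It includes "Participants who present with side-effects that significantly interfere with daily functioning or outweigh therapeutic benefit (CGI Efficacy Scale categorization", and separately lists laboratory, ECG and vital-sign reasons for discontinuation. It sets no time window and does not define tolerant.

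**Analysis form and population, section 20.1.** The outcome is "Toxicity: tolerant vs. non-tolerant". Entry to the clinical outcomes analysis requires at least partial completion: "A partial completion is any participant where at least Research Visit 1, Research Visit 2, Research Visit 3, Intake Visit with Physician, and 6-week Visit". Section 8.2 adds that "those who partially complete the study will be counted toward the 120". Section 11.1 gives the 6-week visit a window of 2 weeks either side, so the shortest admitted follow-up is about 4 to 8 weeks.

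**Contrast with response.** Response is judged after approximately 18 weeks, and early stopping has a rule: "Participants who discontinue ATX prior to the planned end of study (18 weeks) due to perceived lack of efficacy", if it occurs although the dose was raised, makes the child a non-responder. Tolerance has no matching rule.

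**The concern.** Under section 4.2 a child becomes intolerant only through a side-effect stop that happens while the child is under observation. A child who leaves at week 6 because of loss to follow-up, withdrawn assent or lack of benefit receives the same tolerant label as a child observed to week 18. The label therefore mixes two things: how well the drug is tolerated, and how long the child was watched.

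Two results depend on it. One is the intolerance proportion itself, which falls under the primary safety endpoints. The other is the set of comparisons built on the label: Hypothesis 3 (section 2.2) compares tolerant and non-tolerant cohorts on baseline characteristics, and section 20.1 correlates every pharmacodynamic marker with tolerance. If a marker or trait is related to time on drug, it can appear related to tolerance for that reason alone.

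The entry rule adds a further loss. A child who stops for side effects before Research Visit 3 or the 6-week visit is a clear case of intolerance under section 4.2, yet does not meet partial completion and so drops out of the clinical outcomes analysis.

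**Working it through.** The plan states no tolerance rate, power or sample size, so there is no figure of its own to reproduce. The check has two parts.

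**1. Does anything else in the plan account for time at risk?**
- Section 20.1 uses adherence as a confounding factor. Section 11.2 (Research Visit 4) defines adherence as the share of scheduled doses taken. A child who took every dose for 6 weeks is in the high group, so adherence does not measure duration.
- Section 20.2 says weighting or imputation will be considered for attrition, without reference to tolerance. A child with short follow-up is not missing on tolerance, because section 4.2 already supplies the label. Nothing would trigger imputation.
- No time-to-event method, censoring rule or exposure-adjusted rate is given for tolerance.

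**2. How large could the effect be?**

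Inputs from the documents: N = 120 (section 8.2), 18 weeks of planned treatment, minimum follow-up at the 6-week visit.

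Assumptions, because the documents give no values: p18, the proportion intolerant by week 18, is 10%, 20% or 30%; the share s leaving at week 6 for non-safety reasons is 10%, 20% or 30%. The figures count intolerance from first dose and leave out the separate loss of early side-effect stoppers.

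Cumulative intolerance by week t:
- constant hazard: 1 − (1 − p18)^(t/18)
- front-loaded hazard (Weibull shape 0.5): 1 − (1 − p18)^((t/18)^0.5)

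With p18 = 20% and t = 6:
- constant: 1 − 0.8^(1/3) = 7.2%, which is 36% of the 18-week risk
- front-loaded: 1 − 0.8^0.577 = 12.1%, which is 60%

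Over the 4-to-8-week window the constant-hazard figure runs from 4.8% to 9.4%.

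With s = 20%, 24 children leave at week 6 and 96 stay:
- mislabelled, constant: 24 × (0.200 − 0.072) = 3.1
- mislabelled, front-loaded: 24 × (0.200 − 0.121) = 1.9
- crude rate, constant: (96 × 0.200 + 24 × 0.072)/120 = 20.9/120 = 17.4%
- crude rate, front-loaded: (96 × 0.200 + 24 × 0.121)/120 = 22.1/120 = 18.4%

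| p18 | Mislabelled, constant hazard (s = 10%, 20%, 30%) | Mislabelled, front-loaded (s = 10%, 20%, 30%) |
|---|---|---|
| 10% | 0.8, 1.6, 2.4 | 0.5, 1.0, 1.5 |
| 20% | 1.5, 3.1, 4.6 | 0.9, 1.9, 2.8 |
| 30% | 2.3, 4.5, 6.8 | 1.4, 2.7, 4.1 |

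**Between groups.** Suppose the true hazards are equal, p18 = 20%, no responder leaves early, and half the non-responders leave at week 6. Non-responders then show 0.5 × 20% + 0.5 × 7.2% = 13.6% against 20%. If a quarter leave, they show 16.8%. Now let the non-responders' hazard be h times as high: their rate becomes 0.5 × (1 − 0.8^h) + 0.5 × (1 − 0.8^(h/3)). At h = 1.54 this is 20%, so the gap vanishes; at h = 2 it is 24.9%, so the gap reverses.

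**The case against.** **Direction.** A reader might infer that intolerance is understated most in non-responders, so that any marker of non-response will look like a marker of good tolerance. The documents do not support that. Section 5.1 titrates to the higher exposure targets according to response, and section 20.1 describes those who stop for inefficacy as having already been escalated. Non-responders may therefore have higher exposure and a higher hazard, and the calculation above shows that a moderate difference cancels or reverses the bias. The only withdrawal rule for poor response (section 16.1) refers to the 12-week and 18-week visits, and no exit times by response are given. This objection stands. Nor do the documents show that early leavers have usually not reached the higher targets.

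**Size.** Scenarios in which half or more of the non-responders leave between weeks 6 and 12 have no basis in the documents. The half-leaving case above only shows the mechanism and is not an estimate. In the central case the effect is about 2 to 3 children. This also stands.

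**The wider definition.** Under section 20.1 a child with interfering side effects can be intolerant without stopping, so not every early leaver is tolerant by default. That is correct, but it exposes a conflict between two definitions, and neither has a time window.

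**Other safeguards.** Adverse event reporting is a separate outcome, and section 11.2 provides a call two weeks after completion or withdrawal. These help safety surveillance. They do not change the tolerance label or adjust it for time on drug.

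**Conclusion.** The concern holds as a matter of definition. Tolerance has no assessment time in either section, and unequal follow-up is pooled by the entry rule. Wherever children leave early for reasons other than side effects and some risk remains after they go, the crude proportion is too low as an 18-week rate. Comparisons by marker or baseline trait are confounded by time on drug wherever follow-up differs.

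The size is illustrative only: about 2 to 3 of 120 children in the central case, and 0.5 to 6.8 across the assumed ranges. It rests on the assumed intolerance rate, leaver share and hazard shape. No direction can be claimed between responders and non-responders. No power or sample-size statement in the plan is affected.

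The change should be made, because tolerance is a safety endpoint and part of a stated hypothesis, and the better analysis is cheap.

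**What to change.** 1. Reconcile the intolerance definitions in sections 4.2 and 20.1 into one criterion. Which one is a clinical decision for the study team.
2. Use all dosed children as the population, including those who stop for side effects before the 6-week visit.
3. Analyse time from first dose to first meeting the criterion. End follow-up at the last contact on drug, and treat stopping for other reasons as a competing event.
4. Report cumulative incidence of intolerance at week 18, alongside that of other stops. It is the risk of intolerance before any other stop, so competing exits lower it too; it should be labelled that way.
5. For this reason, relate markers and baseline traits to the cause-specific hazard, for example by Cox regression, which compares children at the same time on drug. Report weeks on drug by group.
6. Keep the yes/no label as descriptive only. Do not restrict it to early intolerant children plus 18-week completers: that keeps early cases and drops early non-cases. In the central constant-hazard case it gives 20.9/(20.9 + 96 × 0.8) = 20.9/97.7 = 21.4% against a true 20%.

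**Cost.** SAP wording and a little more analysis. Day 0 is defined in the Schedule of Events, the study booklet holds the medication calendar, and section 16.2 requires withdrawal documentation; the stop date and reason should be made explicit items. One limit remains: the CGI-based criterion is dated only to the visit at which it is rated, so its onset is interval-censored by about 6 weeks.
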